2.3 Subject disposition, demographics and other Baseline characteristics

2.3.1 Subject disposition

The data of subject disposition will be summarized separately for the Main study as below, unless additional details are stated for the mechanistic sub-study treatment and follow-up phase

will be presented. All tables and listings mentioned in this section will be based on the Randomized set. If required, analysis will be also repeated for the mFAS analysis set.

Screening Phase disposition: The number and percentage of subjects screened, completed and discontinued at Screening with the reasons for screen failures will be presented for all enrolled subjects as captured in the Screening log page of the eCRF.

Since multiple attempts of rescreening are allowed, the rescreening data will be handled in the following approach to ensure that an overestimation of the number of screened subjects is not reported:

- If a subject completes after one or more rescreening attempts and is randomized, he/she will be counted only once as screened and Screening completed and not as a screen failed (as he/she has ultimately met the eligibility criteria and entered the treatment phase)
- If a subject fails after one or more rescreening attempts, He/She will be counted only once as screened and once as screen-failed (although he/she might have failed Screening 2 or more times)
- if a subject is rescreened, only the last available Screening data will be reported.

Treatment and follow-up phase disposition: The number and percentage of subjects in the FAS who completed or discontinued the study periods (i.e., treatment phase at Visit 5 including the reason for discontinuation as captured in the eCRF will be presented by treatment.

Study treatment phase completion:

- Subjects who discontinue at Week 52 (for Arm A1 and Arm B1) due to PASI < 50 and at Week 104 (for Arm A2) due to PASI < 90 will be assumed as treatment phase completers and will not enter into the follow-up period
- Subjects who achieve PASI between 50 and 90 at Week 52 (for Arm A1 and Arm B1) will be assumed as treatment phase completers and enter follow-up period till Week 104.

Subjects who complete treatment phase at Week 52 (for Arm A1 and Arm B1) and Week 104 (for Arm A2) but discontinue before entering follow up phase (despite PASI 50/PASI 90 requirement met) will be assumed as treatment phase completers. The Investigator or Staff will fill additional follow-up disposition eCRF with the reason for discontinuation from the study. In this manner, all the reasons for subjects discontinuation from the study will be captured.

In the Main study for final analysis, subject disposition status with reasons for discontinuation as per CRF will be calculated for duration of Baseline – Week 52. Whereas , for follow-up epoch the duration is Week 52 – Week 104 , Week 104 – Week 152 and Week 152 – Week 208 and for entire follow-up epoch duration Week 52- Week 208. An analysis will be performed for Randomized set and follow-up efficacy analysis set.

For the follow-up epoch, an analysis will be repeated from subgroup of subjects who entered follow-up phase , percentage calculations based on the subject entered follow-up phase. Subject disposition in the follow-up phase for the above mentioned duration (Week 52 – Week 104, Week 104 – Week 152, Week 152 – Week 208) is also performed with respect to the PASI categories (PASI 50-89, PASI 75, PASI 90 and PASI 100) at Week 52. An analysis will be performed for mFAS.

For the mechanistic sub-study, subjects disposition over Screening, treatment and follow-up phase are summarized similarly in separate tables at time of Week 52 interim analysis. However, at time of final analysis and if required at time of Week 104 interim analysis treatment arms are presented separately as per [section 2.1](#). For W104 IA and Final analysis subject disposition status with reasons for discontinuation will be calculated for duration of Baseline – Week 52 , Baseline – Week 104 and Week 52 – W104 for Treatment epoch (Arm A2: Week 104) . Whereas , for follow-up epoch the duration is Week 52 – Week 104 (Arm A1 and B1) , Week 104 – Week 152 , Week 152 – Week 208 and Week 52 – Week 208. For the follow-up epoch, an analysis will be repeated for the subgroup of subjects who entered follow-up phase , percentage calculations based on all the subject entered follow-up phase.

Median time to event (i.e. discontinuation) and quartiles including 95% confidence intervals will be provided. The confidence intervals will be based on log-log transformation (PROC LIFETEST option conftype=log-log). Completers will be treated as censored. If any subject whose PASI score is not collected at analysis visit week 52 the subject will be not considered for Time to discontinuation analysis.

In addition, the number and percentage of subjects with protocol deviations will be tabulated by each treatment and deviation category, separately for Main study and Mechanistic sub-study. Subjects excluded from analysis set(s) due to defined Protocol deviations will be tabulated in the same. The number and percentages of subjects in each analysis set will be summarized by each treatment for the FAS, separately for Main study and Mechanistic sub-study. In Mechanistic study for final analysis protocol deviation will be listed only for FAS set. . Covid-19-specific protocol deviations will be tabulated separately in a similar way. Listing will also be produced separately for Covid-19 related protocol deviations.

Caution will be taken in the interpretation of the percentages of subject disposition and protocol deviations due to the overlap of subjects between study arms (A1 and B1) in the Main study and Mechanistic sub-study, as data of these 2 arms will be included in both of the study outputs.

All subjects data related to disposition, protocol deviation and analysis sets will also be listed.

Any possible implications of study changes due to COVID-19 on the interpretation of study subject data will be tabulated and listed.

2.3.2 Demographics and Baseline characteristics

For the Main study and Mechanistic sub-study, summary statistics will be presented for continuous demographic and Baseline characteristic variables by treatment for all subjects in the FAS.

Similarly for categorical variables, the number and percentage of subjects in each category will be presented by each treatment arm for all subjects in the FAS. If required, analysis will be also performed for mFAS.

In Mechanistic substudy at the time of Week 104 IA and Final analysis, only listings will be presented for Demogrphics and Baseline disease characteristics based on FAS. The corresponding summary tables were already included earlier IAs (EX: Week 52 IA).

2.3.2.1 Demographics

Continuous demographic variables captured either at Screening or at Baseline include:

- age (in years; calculated in the eCRF from date of birth and Visit 1 date)
- height at Screening (in centimeters)
- weight at Baseline (in kilograms)
- body mass index (BMI, in kg/m²) = (body weight at Baseline in kilograms) / (height at Screening in centimeters/100)²

For BMI, height and body weight used is the last value prior to randomization. If there is no weight recorded prior to taking of study drug, BMI will be missing.

Categorical demographic variables captured either at Screening or at Baseline include:

- age categories (18-30, 31-50)
- gender (male, female)
- race (Caucasian, Black, Asian, Native American, Pacific Islander, Unknown, Other)
- ethnicity (Hispanic or Latino, East Asian, Southeast Asian, South Asian, West Asian, Russian, Mixed, Not Reported, Unknown, Other)
- child-bearing potential (able to bear child, premenarche, post-menopausal, sterile - of child bearing age)
- skin type (I, II, III, IV, V, VI)
- smoking status at Baseline (never, current, former)
 - estimated number of pack-years (The estimated number of pack years is defined as the total years of smoking multiplied by cigarette packs smoked per day (e.g. 10 pack years = 1 pack /day x 10 yrs., or ½ pack/day x 20 yrs.). The number of pack years will be analyzed as recorded on the eCRF.)
 - Time since last date of tobacco use (for former category) = (Date of Visit 1 – Date of last use of tobacco + 1)/365.25.
- Presence of cardiovascular history (Yes/No)

2.3.2.2 Disease history and Baseline characteristics

In addition, the following variables collected at Baseline (Visit 1) will be summarized by treatment:

- 12-lead electrocardiogram (ECG)vital signs
 - sitting pulse (beats/min)
 - Mean of sitting blood pressure (systolic/diastolic) (mmHg)
- serum pregnancy test (only for women of child bearing potential)

█ [REDACTED]

█ [REDACTED]

- PASI total score
- PASI categories (< 10, 10 - ≤ 20, > 20)
- BSA (affected %)
- IGA mod 2011 score
- Time since the first diagnosis (by a physician) of plaque-type psoriasis (Years) (Visit 1 date is reference date)
- Presence of psoriatic arthritis (Yes/No)
- Time since the diagnosis of psoriatic arthritis (Years) (Visit 1 date is reference date)

Onset of psoriasis time in years will be calculated as:

Treatment start date - date of first diagnosis (by physician) of plaque psoriasis/psoriatic arthritis+1)/365.25

The first diagnosis date will be imputed according to the imputation rules in Section [5.3.3.3](#)

Visit 1 Date is nothing but treatment start date. If treatment start date is missing then randomization date will considered as a reference start date.

2.3.2.3 Relevant medical history / Current medical conditions

Any condition entered as medical history or current medical conditions at Baseline will be coded using the MedDRA dictionary version 26 or later. Medical history will be summarized for all subjects in the FAS by SOC and PT . Summaries for psoriasis-specific medical history will be provided separately. Cardiovascular medical history assessed prior to randomization will also be summarized.

This medical history data will also be listed with ongoing treatments flagged.

2.4 Treatments (study treatment, rescue medication, concomitant therapies, compliance)

2.4.1 Exposure to study treatment and overall compliance

AIN 300mg

The analysis of study treatment data will be based on the SAF. “DOSAGE ADMINISTRATION RECORD” and nb-UVB (Cycle 1, Cycle 2) eCRF page and will be used for below analysis.

The number of secukinumab 300 mg injections will be summarized for Main study and Mechanistic sub-study by treatment arms by means of contingency tables. For Main Study treatment arms are A1a, A1b and for Mechanistic sub-study treatment arms are A1b, A2, C1 and C2.

Duration of exposure to study treatment will be summarized by treatment arms.

In addition, the number of subjects with exposure of at least certain time thresholds will be displayed.

The following categories will be presented: “any exposure” , “≥ 1 week” , “≥ 2 weeks” , “≥ 3 weeks” , “≥ 4 weeks” , “≥ 8 weeks” , “≥ 12 weeks” , “≥ 16 weeks” , and so on with an increase of time threshold by 4 weeks until there are no subjects in the category or the last category “≥ 48 weeks” is presented for Arm A1 in main study and for Arm C1 in mechanistic study. Similarly last category “≥ 100 weeks” is presented for Arm A2 and Arm C2 in mechanistic study.

Duration of exposure will be defined as the time from first dose of study medication to the last dose plus 84 days or last visit (including follow-up visits) whichever occurs earlier. i.e., for subjects who discontinued or have their last visit earlier than 84 days, the end of study treatment exposure will be the date of the last study visit in the follow-up period or in the corresponding treatment period.

Duration of exposure (days) = min (‘end of treatment period’ date, last dose date +84) – first dose date +1

Duration of exposure (years) = duration of exposure (days) / 365.25

Duration of exposure (100 subject years) = duration of exposure (years) / 100

The cumulative actual dose of secukinumab is defined as the sum of all doses of secukinumab taken across a treatment phase of the study. The cumulative assigned dose of secukinumab is defined as the sum of all doses of secukinumab assigned to a subject across a treatment phase of the study.

Cumulative actual dose administered in mg upto Week 16, Week 52 for arms A1a, A1b and C1 and up to Week 104 for arms A2 and C2 will be summarized.

Compliance for secukinumab is defined as actual cumulative dose divided by cumulative assigned dose. Treatment compliance for subjects will be summarized for subjects for 16 weeks, 52 weeks and for A2 104 weeks.

nb-UVB

Subjects in B1a and B1b receive nb-UVB.

The number of sessions in Cycle 1 and Cycle 2 will be categorized into < 24, 24-36 and count in each category will be presented, number of subjects exposed to treatment with nb-UVB to whole body or partial body will also be summarized. The number of subjects required a second cycle also will be presented.

On-treatment exposure to the study treatment will be defined (in days) time (from first dose to the time to the last dose of treatment+84) . Duration of exposure in Cycle 1 and Cycle 2 will be summarized.

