- **Arm B1:** patients with new-onset plaque psoriasis will receive 1 or 2 cycles of nb-UVB of 12 weeks each with a maximum break of 28 weeks between cycles (patients with PASI 90 at Week 40 will not receive a second treatment cycle). Only during the first 4 weeks of each cycle, nb-UVB treatment may be given in combination with topical calcipotriol 50 µg/g and betamethasone 0.5 mg/g

Follow-up Epoch

At the end of the Treatment Epoch at Week 52, all patients with \geq PASI 50 response from Arm A1 and Arm B1 will enter the Follow-up Epoch. Patients who do not achieve a PASI 50 response, will have all assessments of EOS and be discontinued from the study.

During the Follow-up Epoch, patients will not receive study treatment; they will be observed maximally until Week 208, and compared regarding the proportion of them who achieve PASI 90 scores at Week 104.

[figure not shown]
Patients who relapse (those who experience a loss of 50% of the maximum improvement in PASI score achieved during the Treatment Epoch) will have all assessments of EOS and be discontinued from the study.

If no relapse occurs, patients who achieve $<$ PASI 90 at Week 52 in Arms A1 (A1a and A1b) and B1 (B1a and B1b) will be followed (according to the visit schedule outlined in [Table 6-3](#))

until Week 104, while patients who achieve \geq PASI 90 at Week 52 will be followed until Week 208.

The investigator should provide ongoing adequate care for patients who relapse. If the investigator decides to continue treating the patients with secukinumab, a new loading dose of commercially available secukinumab could be considered. The treatment with secukinumab after relapse will be out of scope of the study.

Figure 3-1 Study design – Main Study

BL = baseline, EOS = end of study, KSE = key secondary endpoint, nb-UVB=narrow-band ultraviolet B, PASI = psoriasis area and severity index, PE = primary endpoint, R = randomization.

Mechanistic Sub-study

A separate informed consent will be obtained from study patients who agree on having skin biopsies taken and therefore become eligible for this Mechanistic Sub-study. Besides the biopsies, patients will undergo the same assessments as in the Main Study.

Treatment Epoch

At the baseline visit, eligible patients will be allocated to one of the treatment arms of the Mechanistic Sub-study (see [Figure 3-1](#) and [Section 5.3](#)):

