- **Arm B1:** Subjects with new-onset plaque psoriasis will receive either 1 or 2 cycles of nb-UVB of 12 weeks each with a maximum break of 28 weeks between cycles (subjects with PASI 90 at Week 40 will not receive a second treatment cycle). Only during the first 4 weeks of each cycle, nb-UVB treatment will be given in combination with topical calcipotriol 50 µg/g and betamethasone 0.5 mg/g.

Follow-up Phase

At the end of the Treatment Phase at Week 52, all subjects with \geq PASI 50 response from Arm A1 and Arm B1 will enter the Follow-up Phase. Subjects who do not achieve a PASI 50 response, will have all assessments of end of study (EOS) and be discontinued from the study.

[figure not shown]
During the Follow-up Phase, subjects will not receive study treatment; they will be observed maximally until Week 208, and compared regarding the proportion of them who achieve PASI 90 response at Week 104.

Subjects who relapse (those who experience a loss of 50% of the maximum improvement in PASI score achieved during the Treatment Phase) will have all assessments of EOS and be discontinued from the study.

If no relapse occurs, subjects who achieve $<$ PASI 90 at Week 52 in Arms A1 (A1a and A1b) and B1 (B1a and B1b) will be followed until Week 104, while subjects who achieve \geq PASI 90 at Week 52 will be followed until Week 208.

The investigator should provide ongoing adequate care for subjects who relapse. If the investigator decides to continue treating the subjects with secukinumab, a new loading dose of commercially available secukinumab could be considered. The treatment with secukinumab after relapse will be out of scope of the study.

Figure 1-1 Study design – Main study

BL = baseline, EOS = end of study, KSE = key secondary endpoint, nb-UVB=narrow-band ultraviolet B, PASI = psoriasis area and severity index, PE = primary endpoint, R = randomization.

Mechanistic Sub-study

A separate informed consent will be obtained from study subjects who agree on having skin biopsies taken and therefore become eligible for this Mechanistic Sub-study. Besides the biopsies, subjects will undergo the same assessments as in the Main Study.

Treatment Phase

At the Baseline Visit, eligible subjects will be allocated to one of the treatment arms of the mechanistic Sub-study (see [Figure 1-1](#)):

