2.1.1.4 Day of last dose of randomized study treatment

The date of last dose will be collected via the eCRF. The subject's exposure will be calculated considering the last visit or the last dose + 84 days whichever occurs earlier.

For safety analysis on-treatment is defined as assessments from the first dose to last dose plus 84 days.

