5.2 Exposure adjusted incidence rate and related risk estimates

5.2.1 Exposure adjusted incidence rate and 100*(1-α)% confidence interval

It will be assumed that for each of n subjects in a clinical trial the time t_j ($j=1, \dots, n$) to the first occurrence of a certain treatment emergent event is observed, or if the event was not experienced, the (censored) time to the end of the observation period or last dose plus 84 days whichever occur earlier. The sequence of first occurrences of an event will be modeled to follow approximately a Poisson process with constant intensity θ . The rate parameter θ will be estimated as $\lambda = D/T$, where $T = \sum_{j=1}^n t_j$ and D is the number of subjects with at least one event.

Conditionally on T , an exact 100*(1-α)% confidence interval for a Poisson variable with parameter θT and observed value D can be obtained based on (Garwood, 1936), from which an exact 100*(1-α)% confidence interval for D/T will be derived as follows (Sahai, 1993; Ulm, 1990):

Lower confidence limit $L = \frac{0.5c_{\alpha/2, 2D}}{T}$ for $D > 0$, 0 otherwise,

Upper confidence limit $U = \frac{0.5c_{1-\alpha/2, 2D+2}}{T}$

where $c_{\alpha, k}$ is the α th quantile of the Chi-square distribution with k degrees of freedom.

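### nb-UVB on-treatment time runs unbroken through the between-cycle break, so a patient's status in Weeks 24 to 40 depends on whether a second cycle follows

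*SAP*

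**What the plan says.** SAP 2.4.1, under nb-UVB: "On-treatment exposure to the study treatment will be defined (in days) time (from first dose to the time to the last dose of treatment+84". Nothing is subtracted for time between cycles. The next sentence adds that "Duration of exposure in Cycle 1 and Cycle 2 will be summarized", but no AE rate is tied to those durations.

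The same end point recurs elsewhere:
- SAP 2.1.1.4: "For safety analysis on-treatment is defined as assessments from the first dose to last dose plus 84 days".
- SAP 2.8.1 takes AEs as treatment-emergent from first dose until 84 days after the last dose. SAP 2.8 restricts AE tables to treatment-emergent records, and by-visit laboratory and vital-sign tables to on-treatment records.
- SAP 5.2.1 censors event-free patients at "time to the end of the observation period or last dose plus 84 days whichever occur earlier".

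The regimen in Protocol 3.1 is "1 or 2 cycles of nb-UVB of 12 weeks each with a maximum break of 28 weeks between cycles", and "patients with PASI 90 at Week 40 will not receive a second treatment cycle". Secukinumab in Arm A1 is given every 4 weeks to Week 48 after the weekly induction doses.

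**The concern.** First dose to last dose plus 84 days suits a drug given continuously. nb-UVB comes in one or two blocks, and for a two-cycle patient the window bridges the break between them.

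Two things are at stake. The first is classification. Whether an AE at Week 30 is treatment-emergent, or a Week 36 laboratory value or vital sign is on treatment, depends on whether that patient later starts cycle 2. The Week 36 on-treatment column for B1 would therefore be selected by later treatment, which itself depends on response.

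The second is dilution. Protocol 3.6 names sunburn-type reactions as the main nb-UVB risk. For events tied to sessions, the break adds person-time but few events, which lowers the B1 rate per 100 subject-years. Arm A1 dosed to schedule has no such gap.

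**Working it through.** The documents state no person-time or off-session share, so there is no figure of theirs to reproduce. Their timeline is consistent with a full break: 12 + 28 = 40, the week of the second-cycle decision, and 12 + 28 + 12 = 52, the stated B1 treatment duration. But 28 weeks is a maximum, not an expected value.

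**Per patient.** Let b be the break in weeks.
- Two-cycle window: 12 + b + 12 + 12 = 36 + b. At b = 28 this is 64 weeks.
- Weeks in it more than 84 days (12 weeks) after any session: max(0, b − 12). At b = 28 this is 16 weeks, Weeks 24 to 40; 16/64 = 25.0%.
- One-cycle window: 12 + 12 = 24 weeks, so the patient is off treatment from Week 24.
- Secukinumab: 48 + 12 = 60 weeks. Doses are at most 4 weeks apart, or 8 with the one missed dose that Protocol 5.5.5 allows, so no gap exceeds 12 weeks.

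**Across Arm B1.** Let f be the two-cycle share, which the documents do not give. Assume everyone is observed to last session + 84 days:

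share = f × max(0, b − 12) / [f × (36 + b) + (1 − f) × 24]

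At f = 0.65 and b = 28, the mean window is 0.65 × 64 + 0.35 × 24 = 50.0 weeks. Of these, 0.65 × 16 = 10.4 weeks are off-session, or 20.8%, leaving 39.6 weeks.

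| Break (weeks) | f = 0.30 | f = 0.50 | f = 0.65 | f = 1.00 |
|---|---|---|---|---|
| 12 or less | 0% | 0% | 0% | 0% |
| 16 | 3.7% | 5.3% | 6.2% | 7.7% |
| 20 | 7.1% | 10.0% | 11.6% | 14.3% |
| 24 | 10.3% | 14.3% | 16.5% | 20.0% |
| 28 | 13.3% | 18.2% | 20.8% | 25.0% |

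If two-cycle exposure were instead cut at Week 52, b = 28 gives 10.4 / (0.65 × 52 + 8.4) = 24.6% at f = 0.65, and 16/52 = 30.8% at f = 1.

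**Effect on the first-event rate (SAP 5.2.1), f = 0.65, b = 28.** Take a constant weekly hazard h through each cycle's 24-week window (sessions plus 84 days) and none in the gap. With D the proportion having an event:

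D = 0.65 × (1 − e^(−48h)) + 0.35 × (1 − e^(−24h))

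estimated rate / h = (D/h) / [D/h + 0.65 × 16 × e^(−24h)]

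- h = 0.001: 38.76 / (38.76 + 10.15) = 0.79, understated by about 21%.
- h = 0.05: 16.71 / (16.71 + 3.13) = 0.84, about 16%.
- h = 0.10: 9.63 / (9.63 + 0.94) = 0.91, about 9%.

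Common events are diluted less because many patients have their first event before the gap and contribute no gap time. This depends on the hazard shape. If the hazard is confined to the 12 session weeks of each cycle, the ratio of the continuous-window rate to the per-cycle rate stays at 0.79 to 0.80 over the same values of h.

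For a background AE with the same hazard throughout, gap events enter the numerator as gap time enters the denominator. The ratio is 1.0.

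**The case against.** The strongest defence is that the documents treat the break as part of the regimen. Protocol Table 3-1 gives B1 a 52-week treatment duration, and SAP 2.8 runs the Main Study treatment period from randomization to Week 52. Every statement of the 84-day rule is tied to the last dose. A reader might infer that the SAP breaks its own rule during the gap. It does not: nothing says a patient is off treatment 84 days after an earlier session. This stands, and makes the continuous window a legitimate display. It does not explain why a one-cycle patient on the same 52-week strategy leaves the on-treatment tables at about Week 24.

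A reader might also take 20.8% as the expected figure for Arm B1. It needs the maximum break for every two-cycle patient, no dropout (the plan assumes 20% in B1) and f = 0.65. That f comes from one minus the assumed 35% PASI 90 rate, which applies at Week 52 after one or two cycles, not to the Week 40 decision.

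Nor do all AE rates fall by the same share: common first events can be diluted less, and constant-hazard background AEs not at all. Crude incidence uses no person-time, although the same window decides which AEs it counts. SAP 5.2.2 speaks only of exposure time, so its use of the continuous window is an inference.

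Finally, making per-cycle time the only definition could move delayed harm out of the main table. Skin cancers are AEs of special interest in SAP Table 2-4. That objection stands and shapes the fix.

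**Conclusion.** The point holds as an inconsistency of classification with a bounded effect on rates. It follows from the text alone that Weeks 24 to 40 can be on treatment for one B1 patient and off treatment for another with the same history to date. For a two-cycle patient with the full break, 25% of the window is affected.

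At arm level the documents support only a range, from 0% with breaks of 12 weeks or less to 25% if everyone has two cycles and the full break (30.8% with a cut at Week 52). The 65% figures are scenarios.

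The direction is towards understating session-related nb-UVB AEs in exposure-adjusted rates. A general tilt of the harm comparison against secukinumab is not shown. The primary and key secondary efficacy analyses are unaffected, and no safety hypothesis test is planned.

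**What to change.** Amend SAP 2.1.1.4, 2.4.1, 2.8.1 and 5.2 so that one rule applies to every B1 patient:

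1. Beside the continuous-window display, add exposure-adjusted AE rates and on-treatment summaries with nb-UVB time counted per cycle: from the cycle's first session to the earlier of its last session + 84 days and the start of the next cycle, summed over cycles.
2. Show AEs in the between-cycle or post-cycle-1 gap in their own column, for one-cycle and two-cycle patients alike.
3. Keep delayed events such as skin cancers in the overall treatment-period table, whatever the per-cycle window.
4. State in 5.2.2 which exposure time is meant.

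SAP 2.4.1 already draws on separate Cycle 1 and Cycle 2 eCRF pages, so the cost is SAP wording and programming. The per-cycle display will have fewer B1 person-years and slightly wider B1 intervals. No treatment rule changes.
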